9.9 MANAGEMENT OF DRY EYE SYMPTOMS DURING FOLLOW-UP

During follow-up, subjects should refrain from using any dry eye treatments, including drops, lubricants, warm compresses, etc. If they require "rescue therapy" to relieve their symptoms, they should use the same type of drops or lubricants they were using prior to the study. They should document use of drops or lubricants on the Lubricant/Drop Log.

Subjects should not use Restasis or Xiidra during the study. Use of these drugs will result in the subject being excluded from the "Per Protocol" analysis from the time of initiation of these drugs forward.

Subject should not be treated with other dry eye treatments (e.g. IPL, TrueTear, punctal plugs, etc.) during the course of the study. Administration of these treatments will result in the subject being excluded from the “Per Protocol” analysis from the time of initiation of these treatments forward.

NOTE: If a subject had a punctal plug at the baseline visit and it falls out during the study, it should be replaced.

9.10 WITHDRAWAL AND DISCONTINUATION

All subjects have the right to withdraw at any point during the treatment without prejudice. The investigator can discontinue any subject at any time if continued participation in the study would result in harm to the subject. All efforts should be made by the investigator to retain the subject in the study. If a subject withdraws prematurely from the study, a genuine effort must be made to determine the reason(s) the subject discontinued the study. The reason must be recorded in the subject’s file and on the Study Exit Form.

If a subject withdraws from the study post-randomization but prior to receiving the TearCare or Warm Compress treatment, then that subject may be replaced in the study by a newly enrolled subject.

9.11 SUBJECTS LOST TO FOLLOW-UP

Subjects who do not show up for a follow-up must be contacted to attempt to have them come for the follow-up. For those subjects who cannot be reached, at least 3 phone call attempts should be made and documented. If still no response, a registered letter shall be sent to the address on file for the subject in an attempt to make contact. If a subject misses two consecutive follow-up visits without any contact with the study staff, the subject will be considered lost-to-follow-up unless there is a further communication by the subject.

10 ADVERSE EVENTS (AES)

Adverse Events are defined below. Adverse events that occur in the eye during the trial, whether they are considered to be device related or not, must be documented in the subject’s records. Non-ocular adverse events do not need to be recorded as adverse events unless they meet the definition of serious adverse event or are believed to be related to the study device or a study procedure. Date of the event, its severity, treatment (if any) and the assessed relationship of the event to the study device will be recorded on the Adverse Event Form. Conditions which exist at the time the subject is

enrolled do not need to be recorded as adverse events unless they increase in severity during the study.

10.1 DEFINITIONS OF AE, SAE, SADE, USADE

Adverse Event	Any untoward medical occurrence in a subject who has been treated with the device that does not necessarily have causal relationship with the treatment.
Adverse Device Effect	Any unfavorable and unintended sign (including an abnormal laboratory finding), symptom, or disease that is possibly related to the study device.
Serious Adverse Event (SAE)	Any untoward medical occurrence that: 
• Results in death• Is life-threatening• Requires in-patient hospitalization or prolongs existing hospitalization• Necessitates medical or surgical intervention to preclude permanent impairment of a body function or permanent damage to a body structure• Sight threatening
Unanticipated Adverse Device Effect	Any serious adverse effect on health or safety, any life-threatening problem or death caused by, or associated with a device if that effect, problem, or death was not previously identified in nature, severity, or degree of incidence in the clinical investigational plan; or any other serious problem associated with a device that relates to the rights, safety, or welfare of subjects (21 CFR 812.3(s)). Any sight-threatening event, whether listed in the protocol or not, is considered to be reportable as a UADE

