10.2 LIST OF ANTICIPATED POTENTIAL ADVERSE EVENTS

Anticipated potential adverse events include those that might reasonably be expected to occur in this study because they are associated with dry eye disease, the risk analysis for TearCare System (albeit remote likelihood) or study testing methods.

- Eyelid/eye pain requiring discontinuation of the procedure
- Eyelid/eye pain ≥ 1 day after the procedure
- Burn, erythema, or swelling of the eyelids
- Thermal injury to the eye, including conjunctiva, cornea or lens
- Physical pressure-induced injury to the eyelid

- Corneal deformation
- Foreign body sensation
- Formation of a chalazion or stye
- Infection of the eyelid or ocular surface
- Ocular surface irritation or inflammation (e.g. Conjunctival injection, conjunctival or corneal abrasion, chemosis)
- Allergic or inflammatory reaction to the SmartLid or LipiFlow activator
- Loss in BCVA (ETDRS) of ≥ 10 letters

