10.3 REPORTING ADVERSE EVENTS AND UNANTICIPATED ADVERSE DEVICE EFFECTS

Identification, collection and reporting of adverse event information is the responsibility of the principal investigator. The investigator records the date of the event, its severity, treatment (if any) and the assessed relationship of the event to the study device on the Adverse Event Case Report Form (AE CRF).

Any ocular-related **serious adverse event** (SAE) should be reported to the study sponsor within one working day of learning of the event. Non-ocular-related SAEs should be reported to the study sponsor within two working days of learning of the event. Email the AE CRF to [REDACTED].

Any **unanticipated adverse device effects (UADE)** must be reported to the following two entities:

1. The study sponsor – Within one working day of the investigator first learning of the event, e-mail the AE CRF to [REDACTED]; and
2. The reviewing IRB – As soon as possible, but no later than 10 working days after the investigator first learns of the event, report per the IRB's instructions.

The sponsor will conduct an evaluation of unanticipated adverse device effects. If the sponsor determines that an unanticipated adverse device effect presents an unreasonable risk to subjects, parts of the investigation presenting risks will be terminated. Termination will occur no later than 5 working days after the sponsor

makes such a determination and no later than 15 working days after the sponsor first received notice of the effect.

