12.6.3 PRIMARY SAFETY ANALYSIS

All adverse events will be reported by treatment group and AE category. Any serious adverse events will be completely described in the study report. The primary safety endpoint will be summarized for each treatment group.

We will compute the incidence of ocular events in two ways: first as a simple proportion, counting the number of subjects with any event (that is, counting the first event per person in either eye), then as an incidence rate, counting all events including repeated events per subject.

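### The SAE definition in Section 10.1 covers events treated to prevent permanent damage but omits events that result in permanent damage, so a lasting eyelid or gland injury can be classed as non-serious

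*Combined protocol and SAP*

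**What the plan says.** The table in Section 10.1 of the protocol lists five ways in which an adverse event becomes serious. Three are death, threat to life, and a new or longer hospital stay. The others are that the event "Necessitates medical or surgical intervention to preclude permanent impairment of a body function or permanent damage to a body structure", or that it is "Sight threatening".

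Section 10.2 lists anticipated events. They include "Burn, erythema, or swelling of the eyelids", pressure injury to the eyelid, and thermal injury to the eye, including the lens.

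Sections 10 and 10.3 name the same four items to be kept for each event. Section 10.3 puts this duty on the site, which "records the date of the event, its severity, treatment (if any) and the assessed relationship of the event to the study device".

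Two consequences follow from serious status. Section 10.3 asks for ocular serious events to reach the sponsor within one working day, and non-ocular ones within two. Section 12.6.3 states: "Any serious adverse events will be completely described in the study report". Other events are tabulated by treatment group and category.

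**The concern.** The fourth criterion makes an event serious when somebody intervenes to prevent permanent harm. The list says nothing of an event in which the permanent harm occurs. Read literally, an eyelid injury treated in time is serious, while the same injury left alone until the damage is permanent is not, unless another criterion applies.

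The omission falls where the risk in this trial lies. TearCare heats the lids at 41 to 45°C and is followed by forceps expression of all four lids. LipiFlow applies heat and pressure to the lids. Lasting damage to a lid or its glands need not threaten sight and need not lead to a hospital stay.

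Demonstrating safety is part of the study objective and supports a new indication. A report that no serious events occurred should mean that no permanent device injury occurred, and under the present wording it need not mean that.

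**Working it through.** The point is one of classification, so the check is to run events through the stated criteria. The events are hypothetical. Section 10.2 names the types (burn, pressure injury, thermal injury) but does not describe scarring, gland loss or lens opacity.

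| Event | Death | Life-threatening | Hospital | Treated to prevent permanence | Sight-threatening | Serious under 10.1? |
|---|---|---|---|---|---|---|
| A. Lid injury, treated to prevent lasting damage, heals | no | no | no | yes | no | yes |
| B. Same lid injury, untreated, damage permanent | no | no | no | no | no | **no** |
| C. Permanent lid damage with hospital stay | no | no | yes | no | no | yes |
| D. Corneal or lens injury that threatens sight | no | no | no | no | yes | yes |

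Only row B escapes, and it is a worse outcome than row A.

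**Does the unanticipated adverse device effect (UADE) route catch row B?** The definition in 10.1 has three relevant parts.

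1. A serious effect not previously identified in nature, severity or incidence. Section 10.2 lists the type of event but mostly gives no severity, so a permanently scarring burn could be argued to be unidentified in severity. It must still be a serious effect.
2. Any other serious problem associated with the device. This again needs a judgement of seriousness.
3. Any sight-threatening event, listed or not. Row B does not threaten sight.

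Parts 1 and 2 can catch row B only if someone judges it serious, and the protocol's only stated criteria for seriousness do not lead there.

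**What changes for row B?** It can miss the one-working-day report in 10.3 and the full description in 12.6.3. It stays in the tables by group and category.

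**Does any planned figure change?** The plan gives no figure for serious events. Its only safety calculation is in SAP Section 22.3.3:

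- Subjects: 100 + 138 = 238. Half to TearCare: 238 / 2 = 119. Eyes: 119 × 2 = 238.
- Exact one-sided 95% upper limit for x events in n eyes: the 0.95 quantile of Beta(x + 1, n − x). With n = 238 it is below 6% for x of 8 or fewer.
- P(X ≤ 8) for a binomial with n = 238 and p = 0.02 is 0.948, against a stated value of approximately 0.95.

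The figure reproduces. It concerns ocular adverse events of any seriousness, as does the primary safety endpoint in Sections 12.6.2 and 22.2.2, so reclassifying row B leaves it as it is.

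**The case against.** The best defence is that little escapes. Intervention to prevent permanence, hospital stay and threat to sight are all covered, and the UADE wording offers a further route. With one month of follow-up, permanence may often be impossible to establish on study. All of this narrows the gap. It does not remove row B.

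A reader might also infer four stronger claims, which the documents do not support.

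- *That the adverse event record has no outcome or end date.* Sections 10 and 10.3 name four items but do not say that these are the only ones, and the form itself is not in the documents. Section 18.3.3 also asks for all relevant observations on adverse device effects. What can be said is that the protocol text does not specify these two items.
- *That harm persisting at Month 1 goes unseen.* Table 3 schedules slit lamp examination, visual acuity, intraocular pressure, staining, gland scoring and adverse event assessment at that visit. Many lasting findings would be in the data, although the slit lamp method in Section 21.3 does not name the lens.
- *That one misclassified event would alter a statistical conclusion on safety.* The plan has no hypothesis, confidence limit or decision rule for serious events.
- *That a continuing event would be counted repeatedly* where Section 12.6.3 computes incidence "then as an incidence rate, counting all events including repeated events per subject". A continuing event has one event date, and nothing in the documents implies recounting it at each visit. SAP Section 22.2.3 specifies only the proportion of subjects with any event, which repeats cannot inflate.

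**Conclusion.** The point holds in a limited form. Section 10.1 omits events that result in permanent impairment or damage. An untreated, non-hospitalized, non-sight-threatening but permanent lid or gland injury is therefore non-serious by the stated rule.

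For such events the effect is confined to seriousness classification, expedited reporting and narratives. The ocular adverse event incidence and the effectiveness analyses are unchanged. The documents give no basis for estimating how many events would be affected.

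The conclusion assumes that investigators apply the five criteria as written, and that a lid injury counts as an ocular event, as the list in 10.2 suggests. If it were handled as non-ocular, the report at stake would be the two-working-day one. The change should be made, but the point is not a threat to the trial's main conclusions.

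**What to change.** 1. In Section 10.1, add a sixth criterion: the event results in permanent impairment of function or permanent structural damage.
2. Apply it to events already recorded in both cohorts. SAP Section 22.2.3 summarizes the primary safety endpoint by cohort and overall, and seriousness should mean the same thing in each.
3. To make the criterion workable, name outcome and resolution date among the recorded items in Sections 10 and 10.3, if the adverse event form does not already hold them.

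The cost is one line of definition, at most two form items, a short re-review of Cohort 1 events, and possibly a slightly higher count of serious events. Because follow-up ends at one month, permanence will sometimes rest on the investigator's judgement at exit. Sample size, endpoints and treatment procedures are untouched.

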10.2 LIST OF ANTICIPATED POTENTIAL ADVERSE EVENTS

Anticipated potential adverse events include those that might reasonably be expected to occur in this study because they are associated with dry eye disease, the risk analysis for TearCare System (albeit remote likelihood) or study testing methods.

- Eyelid/eye pain requiring discontinuation of the procedure
- Eyelid/eye pain ≥ 1 day after the procedure
- Burn, erythema, or swelling of the eyelids
- Thermal injury to the eye, including conjunctiva, cornea or lens
- Physical pressure-induced injury to the eyelid

- Corneal deformation
- Foreign body sensation
- Formation of a chalazion or stye
- Infection of the eyelid or ocular surface
- Ocular surface irritation or inflammation (e.g. Conjunctival injection, conjunctival or corneal abrasion, chemosis)
- Allergic or inflammatory reaction to the SmartLid or LipiFlow activator
- Loss in BCVA (ETDRS) of ≥ 10 letters

10.3 REPORTING ADVERSE EVENTS AND UNANTICIPATED ADVERSE DEVICE EFFECTS

Identification, collection and reporting of adverse event information is the responsibility of the principal investigator. The investigator records the date of the event, its severity, treatment (if any) and the assessed relationship of the event to the study device on the Adverse Event Case Report Form (AE CRF).

Any ocular-related **serious adverse event** (SAE) should be reported to the study sponsor within one working day of learning of the event. Non-ocular-related SAEs should be reported to the study sponsor within two working days of learning of the event. Email the AE CRF to [REDACTED].

Any **unanticipated adverse device effects (UADE)** must be reported to the following two entities:

1. The study sponsor – Within one working day of the investigator first learning of the event, e-mail the AE CRF to [REDACTED]; and
2. The reviewing IRB – As soon as possible, but no later than 10 working days after the investigator first learns of the event, report per the IRB's instructions.

The sponsor will conduct an evaluation of unanticipated adverse device effects. If the sponsor determines that an unanticipated adverse device effect presents an unreasonable risk to subjects, parts of the investigation presenting risks will be terminated. Termination will occur no later than 5 working days after the sponsor

makes such a determination and no later than 15 working days after the sponsor first received notice of the effect.

11 RISK-BENEFIT ANALYSIS

11.1 ANTICIPATED CLINICAL BENEFITS

The TearCare™ procedure will be performed with the aim of reducing the signs and symptoms of dry eye. The goal of the procedure is to provide a safe, reproducible, and effective treatment for dry eye disease, a disease for which there is an unmet need for effective therapies.

11.2 ANTICIPATED ADVERSE DEVICE EFFECTS

Anticipated adverse effects associated with the TearCare System have been described above in Section 10.2.

11.3 RESIDUAL RISKS ASSOCIATED WITH THE TEST DEVICE, AS IDENTIFIED IN THE RISK ANALYSIS REPORT

Sight Sciences believes that there are no Intolerable residual risks from this non-invasive, controlled heat treatment device that can be easily and quickly removed by the subject or by the supervising ophthalmologist, in the event of a complication during a TearCare treatment session.

11.4 RISKS ASSOCIATED WITH PARTICIPATION IN THE CLINICAL INVESTIGATION

All anticipated study risks are listed in Section 10.2.

11.5 POSSIBLE INTERACTIONS WITH CONCOMITANT MEDICAL TREATMENTS

It is anticipated that there will be no interactions with concomitant medical treatments.

11.6 STEPS THAT WILL BE TAKEN TO CONTROL OR MITIGATE THE RISKS

The major risks to the subjects and the steps taken to control or mitigate them are described below:

1. Overheating of the eyelids: All TearCare treatments will be done in the investigator's office under direct supervision of the investigator. The device

delivers heat to the eyelids at a temperature ranging from 41-45°C. This temperature range was selected because it is both safe for eyelid heating and effective for melting obstructions in the meibomian glands.^{43,44,45,46} The user can adjust the temperature up or down to a level that is comfortable, and may also shut off the System at any time if it is too uncomfortable or painful. In addition, the TearCare System continuously monitors and regulates the temperature at the tissue-contacting surface of the SmartLid devices and has been designed to not exceed the maximum allowable temperature.

2. **Corneal abrasion:** If the SmartLid devices are not positioned properly or come loose during the treatment, there is the potential for a corneal abrasion. To mitigate this, the supervising physician will apply the strips to the subject and will monitor their position during the treatment to ensure they remain in place and secure.

In addition, there is the possibility of corneal abrasion or abrasion of the eyelid surface during expression of the meibomian glands. To reduce the chance of abrasion, the forceps have been designed with smooth surfaces (i.e. no rough edges) and only trained users will perform expression.

In addition to the above, the following mitigation steps have also been taken to reduce the risks in this study:

- The device has been tested to demonstrate that it meets performance and safety specifications, as described in Section 5.1.
- Instructions for Use are provided with each device.
- The clinician using the device will be trained in how to safely and correctly apply and remove the SmartLid devices, and operate the TearCare System.
- The clinician will be trained in how to perform meibomian gland expression using the TearCare Clearance Assistant
- The study staff will be trained to perform procedures required in this protocol

⁴³ Lane SS, Dubiner H, Epstein RJ, et al. A New System, the LipiFlow, for the Treatment of Meibomian Gland Dysfunction. *Cornea*. 2012; 31 : 396-404

12 STATISTICAL CONSIDERATIONS

12.1 EVALUABILITY

All subjects on whom the TearCare or LipiFlow is attempted will be considered evaluable for the safety analysis. All eyes that have at least one follow-up visit and have no major protocol deviations will be evaluable for the per protocol analysis.

12.2 ANALYSIS POPULATIONS

The per-protocol analysis population includes all subjects who have at least one follow-up visit and have no major protocol deviations, including specifically no use of dry-eye medications (Xiidra, Restasis). The primary and secondary endpoint analysis will be performed based on the Cohort 2 per-protocol population.

The intent-to-treat (ITT) analysis population includes all subjects who are randomized to either arm, regardless of treatment received. As a sensitivity analysis, the primary and secondary endpoint analyses will also be carried out on the Cohort 2 ITT population as well.

The effectiveness outcomes for Cohort 1 subjects will be summarized descriptively based on the available data of the per-protocol population. The effectiveness data listings will be Cohort 1 subjects that are excluded from in the per-protocol population will be provided separately.

12.3 SUBJECT ACCOUNTABILITY

A complete accounting of subjects by Cohort and visit will be provided, including reasons for dropout, if known.

12.4 DEMOGRAPHICS AND BASELINE CHARACTERISTICS

Demographic variables gender, race, ethnicity, and age will be summarized for all enrolled subjects, along with medical history, by Cohort and combined. Descriptive statistical summaries of pre-treatment parameters (min, max, median, mean, standard deviation) will also be provided for each treatment arm. This includes baseline measurements for each of the study endpoints: TBUT, Total Meibomian Gland Secretion Score, Number of Meibomian glands with any/clear liquid, Corneal Staining, Conjunctival Staining, OSDI Score, SANDE Score, and Eye Dryness Score.

All baseline measurements will be evaluated for adequate balance between the two treatment arms.

12.5 EFFECTIVENESS ENDPOINTS AND ANALYSIS METHODS

All primary and secondary endpoints will be evaluated at 1 month. Outcomes measured on a per-eye basis will be analyzed using data from both eyes, with linear mixed effect models to account for within-person correlation (correlation between right and left eyes).

12.5.1 DESCRIPTIVE ANALYSES

All outcome measures, IOP outcomes, and Use of dry eye lubricants, will be tabulated by visit and treatment group.

